#### 12.1.1 Treatment Administration

Table 12.1.1.1 Number of cycles administered and dose intensity

No. of cycles administered per patient	N	%
1		
2		
3		
...		
Median (range)		
Time on treatment* (weeks)		
Median		
Range		
PM01183 cumulative dose (mg)		
Median		
Range		
PM01183 dose intensity (mg/wk)		
Median		
Range		
PM01183 relative dose intensity (%)		
Median		
Range		

(\*)Time on treatment: defined as last infusion date plus 30 days, or date of death or subsequent therapy (whichever comes first) minus first infusion date.

#### 12.1.2 Cycle Delays

##### 12.1.2.1 Number of Patients and Cycles with Dosing Delay, Any Relationship

Listing 12.1.2.1.1 Delays

Patient id.	Delayed cycle	Delayed cycle start date	Previous cycle	Previous cycle start date	Dose Delay calculated. (days)	Reason for dose delay	Dose Delay Spec.

Table 12.1.2.1.2 Number of patients and cycles with dosing delay, any relationship

	N	%
No. of patients treated		
No. of patients susceptible to have any dose delayed		
No. of patients with any dose delayed		
No. of cycles administered		
No. of cycles susceptible to be delayed*		
No. of cycles with dosing delay**		
No. of patients with		
No cycles delayed		
1 cycle delayed		
2 cycles delayed		
≥ 3 cycles delayed		

(\*) All cycles excluding first cycle. (\*\*) Denominator= Number of cycles susceptible to be delayed

Table 12.1.2.1.3 Number of patients and cycles with dosing delay according to the relationship

	Treatment-related**		Non-treatment-related	
	N	%	N	%
No. of patients with				
1 cycle delayed				
2 cycles delayed				
≥ 3 cycles delayed				
No. of cycles with				
dosing delay*				

(\*) Denominator= Number of cycles susceptible to be delayed. (\*\*)Hematological reason, non-hematological reason or both

Table 12.1.2.1.4 Number of patients and cycles with dosing delay according to the relationship

Reasons for delays		N	%
Cycles	No. of cycles with dosing delays*		
	Treatment-related	X	XX.X
	Hematological		
	Non-hematological		
	Both		
	Non-treatment-related		
Patients	No. of patients with dosing delays*		
	Treatment-related	X	XX.X
	Hematological		
	Non-hematological		
	Both		
	Non-treatment-related		

(\*) Denominator= Number of patient/cycles susceptible to have a delay.

Table 12.1.2.1.5 Length of dosing delay.

Length of delay	Median (range)	Treatment-related**		Non-treatment-related		Total	
		N	%	N	%	N	%
Length of delay*							
<= 7 days							
> 7 days and <=14 days							
> 14 days							

(\*) Denominator= Number of cycles susceptible to be delayed. (\*\*)Hematological reason, Non-hematological reason or both

### 12.1.2.2 Number of Delays According to Cycle Number

Table 12.1.2.2.1 Number and reasons of delays according to cycle number

	No. of patients		No. of delays		Treatment-related*		Treatment-related				Non-treatment-related*	
							Hematological reason		Non-hematological reason		Both	
	N	%	N	%	N	%	N	%	N	%	N	%
Cycle 2												
...												
Cycle 6												
...												

(\*) Denominator= Number of cycles susceptible to be delayed.

Table 12.1.2.2.2 Dose reduction in cycles delayed

		Reduction			
		Yes		No	
		N	%	N	%
Cycle 2					
...					
Cycle 6					
...					
Total					

The distribution of delays according to the cycle administered will be studied by means of counts and percentages. The reasons for cycle delay will be detailed, specifying how many were due to treatment or not.

### 12.1.2.3 Cycle delays due to AEs

Patient id.	Cycle	Preferred term code	Adverse event reported (verbatim)	Grade	Relationship	Onset date	Resolved date	No. of days with delay	Action taken	Significant consequences

AEs with action = 'Dose delayed' or 'Reduced and delayed'.

### 12.1.3 Dose Reductions

All dose reductions should be considered and described, specifying the reason for reduction (hematological toxicity, non-hematological toxicity or other causes).

#### Listing 12.1.3.1 Dose reductions

Patient id.	Cycle	Day	Cycle start date	Previous dose	Reduced dose	Reason for dose reduction	Dose reduction Spec.

Table 12.1.3.2 Number of patients and cycles with dose reduction, any relationship

	N	%
No. of patients treated	X	XX.X
No. of patients susceptible to have a dose reduced		
No. of patients with any dose reduced		
No. of patients with:		
No PM01183 reduction		
1 cycle with PM01183 dose reduced		
2 cycles with PM01183 dose reduced		
No. of cycles administered		
No. of cycles susceptible to have any dose reduced*		
No. of cycles with PM01183 dose reduced **		
No. of cycles with PM01183 dose reduced (Treatment-related)**		

(\*) All cycles excluding first cycle. (\*\*) Denominator= Number of cycles susceptible to have a dose reduction

Table 12.1.3.3 Number of patients and cycles with dose reduction according to the relationship

Reasons for reductions	N	%
Cycles	No. of cycles with dose reductions*	
	Treatment-related	X XX.X
	Hematological	
	Non-hematological	
	Both	
	Non-treatment-related	
Patients	No. of patients with dose reductions*	
	Treatment-related	X XX.X
	Hematological	
	Non-hematological	
	Both	
	Non-treatment-related	

(\*) Denominator= Number of patient/cycles susceptible to have a dose reduction.

Table 12.1.3.4 Number and reasons of reductions according to cycle number

	No. of patients	No. of cycles with reduction	Treatment-related*	Treatment-related			Non-treatment-related*
				Hematological reason		Non-hematological reason	
				N	%	N	
Cycle 1							
Cycle 2							
...							
Cycle 6							
...							

(\*) Denominator= Number of cycles susceptible to be reduced.

Listing 12.1.3.5 Dose reductions due to AEs

Patient id.	Total no. of cycles	Cycle	Preferred term code	Adverse event reported (verbatim)	Grade	Relationship	Onset date	Resolved date	Action taken	Significant consequences

AEs with action = 'Dose reduced/adjusted' or 'Reduced and delayed'.

#### **12.1.4 Infusions Temporarily Interrupted**

A listing of the patients who had infusions temporarily interrupted with the corresponding reasons will be provided.

Listing 12.1.4.1 Interrupted infusion listing.

Patient id.	Cycle	Reason

#### **12.1.5 Prophylactic Medication Administration**

A listing of the patients who have not received corticosteroids, 5-HT antagonists, prokinetics and other antiemetics or equivalents with the corresponding reasons will be reported.

Listing 12.1.5.1 Patients and cycles with prophylactic medication not taken per protocol

Patient id.	Cycle	Prophylactic medication not taken*	Reason
...		No	

(\*) Corticosteroids, 5-HT antagonists, prokinetics and other antiemetics.

### **12.2 Adverse Events**

#### **12.2.1 Adverse Events**

As far as all the toxicities are concerned, the NCI-CTC grade will be used wherever an NCI-CTC grading exists. Otherwise, the severity will be noted. As a convention, the term «Grade» will always be used. Toxicities will be described according to the worst NCI-CTC grade or, for toxicities which do not form the subject of NCI-CTC classification, according to the worst severity.

Adverse events will be described in this section; treatment-related events (stated as related to the study drug or of unknown relationship) will be tabulated.

Type of toxicity and worst grade or severity by cycle and by patient will be summarized according to the Preferred Term coded with MedDRA. Tables will be organized per category of events using System Organ Class of MedDRA.

Subgroup analysis will be performed according to starting dose (7 mg FD vs. 3.5 mg/m^2) and Cohort.

The groups will include:

- Patient treated at 7 mg FD Cohort B
- Patient treated at 7 mg FD Cohort A
- Patient treated at 7 mg FD any Cohort
- Patient treated at 3.5 mg/m^2 Cohort A
- Patient treated at 3.5 mg/m^2 Cohort A1
- Patient treated at 3.5 mg/m^2 any Cohort

The tables will be annotated by adding a letter as suffix.

The tables included in the subgroup analysis are the following:

Table 12.2.2.2 Treatment related AEs. Worst grade by patient

Table 12.2.2.3 Treatment related AEs. Worst grade by cycle

Table 12.2.2.4 Adverse events regardless of relationship. Worst grade by patient

Table 12.2.2.5 Adverse events regardless of relationship. Worst grade by cycle

If clinically relevant the outputs could be split by initial dose or any other characteristic.

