1.3. STUDY RATIONALE

Metastatic breast cancer (MBC) is a clinically heterogeneous and an aggressive disease from which most patients will ultimately die. Unfortunately a cure by the means of currently available treatment options still seems an elusive goal. Cytotoxic chemotherapy remains a crucial component of the therapeutic armamentarium and there is a need to develop more selective approaches to identify subgroups of patients with higher tumor sensitivity that may benefit the most.

PM01183 is a new chemical entity that induces double-strand DNA breaks through binding to the DNA minor groove. Results of the COMPARE analysis (20) revealed that is unlikely that this drug shares a similar mechanism of action with any of the other 98 standard cytotoxic agents compared.

PM01183 has significant *in vitro* and *in vivo* wide antitumor activity, particularly in several breast cancer models.

PM01183 exposure primarily induces DNA damage, particularly to homologous recombinant deficient cells *in vitro* (see IB); thus, patients with BRCA deleterious mutation might be more sensitive to its antitumor effects than other patients. In order to test this hypothesis, two cohorts of patients with advanced breast cancer will be prospectively evaluated in the trial according to their germline BRCA1/2 mutation status: known mutation (BRCA+, Cohort A) *vs.* unselected (BRCA- or -UK, Cohort B). The goal of the trial is, on one hand, to find out whether the presence of a BRCA 1/2 mutation in Cohort A is associated with a higher response rate in MBC patients; and, on the other hand, to explore and benchmark the activity of PM01183 in MBC unselected patients. The study design has taken into account the higher sample heterogeneity of Cohort B by planning the recruitment of more patients in this group. Also, according to the BRCA status in the trial setting, a response rate of 40% or more in Cohort A (sample of patients with known deleterious BRCA 1/2 mutations) will be considered clinically worthy of further research, as well as a response rate of 25% or more in Cohort B.

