3.2. SECONDARY

- To further characterize the antitumor activity of PM01183 in terms of duration of response (DR), clinical benefit [ORR or stable disease lasting over three months (SD > 3 months)], PFS, and one-year overall survival (1y-OS).
- To evaluate whether the presence of a known germline mutation in BRCA 1/2 predicts response to PM01183 in MBC patients.
- To explore the activity of PM01183 in specific breast cancer subpopulations according to hormonal receptor status, HER-2 overexpression, number and/or type of prior therapies, or according to other available histological/molecular classifications/parameters.
- To evaluate the safety profile of this PM01183 administration schedule (Day 1, q3wk) in this patient population.
- To analyze the pharmacokinetics (PK) of PM01183 in this patient population.
- To explore PK/PD (pharmacokinetic / pharmacodynamic) correlations, if applicable.
- To evaluate the pharmacogenomic (PGx) expression profile of selected putative markers potentially predictive of response to PM01183, in tissues from tumor samples.

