5.2. ADMINISTRATION OF STUDY MEDICATIONS

5.2.1. Route of administration, starting dose, and schedule

Patients included under protocol versions 1.0 and 2.0 will receive PM01183 i.v. as a one-hour infusion on Day 1 q3wk at a starting dose of 7.0 mg FD (three weeks = one treatment cycle).

Patients included from protocol version 3.0 onward (after implementation of amendment no. 2) will receive PM01183 i.v. as a one-hour infusion on Day 1 q3wk at a starting dose of 3.5 mg/m² (three weeks = one treatment cycle). Dose will be capped at BSA of 2.0 m² (i.e., dose will not exceed 7 mg). BSA will be calculated according to standard practice at each center.

PM01183 will be administered over a minimum total volume of 100 ml of solution for infusion (either on 5% glucose or 0.9% sodium chloride) through a central catheter or over a minimum total volume of 250 ml if through a peripheral line, always over one hour at a fixed infusion rate.

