8.3.1. Efficacy Analyses

For the primary endpoint (ORR) the exact binomial estimator and its 95% CI will be used.

The time-to-event variables (DR, PFS and OS) and their set time estimates (e.g., PFS3, PFS6 and 1y-OS) will be analyzed according to the Kaplan-Meier method.

Exploratory comparison of the efficacy results between the two study cohorts will be performed by means of Fisher analysis and logistic regression (ORR), and of log-rank test/Cox regression (time-to-event variables). Additionally, if clinically appropriate, the two cohorts might be pooled into one, whenever differences between cohorts are considered not relevant. In such case, the point estimates and their 95% CIs will be also reassessed in order to obtain more accurate calculations.

Exploratory subgroup analyses (e.g., triple negative, hormonal receptor status, HER-2 overexpression, etc.) will be also performed depending on the sample sizes of each subgroup, if appropriate.

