#### ***3.2 Secondary Objectives***

- To further characterize the antitumor activity of PM01183 in terms of duration of response (DR), clinical benefit [ORR or stable disease lasting over three months (SD  $> 3$  months)], PFS, and one-year overall survival (1y-OS).
- To evaluate whether the presence of a known germline mutation in BRCA1/2 predicts response to PM01183 in MBC patients.
- To explore the activity of PM01183 in specific breast cancer subpopulations according to hormonal receptor status, HER-2 overexpression, number and/or type of prior therapies, or according to other available histological/molecular classifications.
- To evaluate the safety profile of this PM01183 administration schedule (Day 1, q3wk) in this patient population.
- To analyze the pharmacokinetics (PK) of PM01183 in this patient population.
- To explore PK/PD (pharmacokinetic / pharmacodynamic) correlations, if applicable.
- To evaluate the pharmacogenomic (PGx) expression profile of selected putative markers potentially predictive of response to PM01183, in tissues from archived tumor samples.

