All variables with a good percentage of valid cases (approximately  $\geq$  90%) and with a p-value lower than 0.10 in the univariate analysis will be included in the exploratory multivariate analysis. Within the multivariate stepwise Logistic/Cox regression analysis, the chosen significance level for entering an explanatory variable into the model will be 0.05 (for all variables not in the model, the one with the smallest p-value is entered if the p-value is less than or equal to the specified significance level). The significance level for removing an explanatory variable from the model is 0.05 (for all variables in the model, the one with the largest p-value will be removed if the p-value exceeds the specified significance level). The parameter estimates, hazard ratios and p-values for hazard ratios of the variables retained in the model will be presented.

If appropriate, multivariate analysis will be produced for a relevant subgroup of patients (e.g. by cohort).

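### The exploratory Cohort A versus Cohort B comparison is probably partly confounded with starting dose, and the SAP guarantees no same-dose or dose-adjusted estimate

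*SAP*

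**What the plan says.** **The question.** Protocol 1.3 opens its statement of aims with "The goal of the trial is, on one hand, to find out whether the presence of a BRCA 1/2 mutation in Cohort A"; the question there is whether carriers respond more often. Protocol 3.2 and SAP 3.2 make this a secondary objective: "To evaluate whether the presence of a known germline mutation in BRCA 1/2 predicts response to PM01183 in MBC patients".

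**The dose.** Protocol 5.2.1 assigns dose by protocol version, not by cohort. Versions 1.0 and 2.0 use a "starting dose of 7.0 mg FD (three weeks = one treatment cycle"). For later patients: "Patients included from protocol version 3.0 onward (after implementation of amendment no. 2) will receive PM01183 i.v. as a one-hour infusion" at 3.5 mg/m2, with BSA capped at 2.0 m2. SAP 14.1 dates amendment no. 2 to October 2014.

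**Dose by cohort.** The safety groups in SAP 12.2.1, repeated for laboratory data in SAP 12.4, include "Patient treated at 7 mg FD Cohort B", Cohort A at 7 mg FD, Cohort A at 3.5 mg/m2 and Cohort A1 at 3.5 mg/m2. No group is listed for Cohort B at 3.5 mg/m2.

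**The comparison.** Protocol 8.3.1: "Exploratory comparison of the efficacy results between the two study cohorts will be performed by means of Fisher analysis and logistic regression (ORR"), with log-rank and Cox methods for time-to-event variables. SAP 6.2.2 allows a supportive log-rank or Cox comparison of cohorts. Neither text restricts or stratifies by dose.

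**Where dose does appear.** SAP 6.2.2 names initial dose among the covariates for multivariate models, to be fitted if appropriate. A variable needs a univariate p-value below 0.10, and then "the chosen significance level for entering an explanatory variable into the model will be 0.05", with removal at the same level. SAP 8.9 and 11.3 plan efficacy subgroup tables by starting dose within Cohort A, and Table 11.1.12.5 compares baseline characteristics by dose in that cohort.

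**The concern.** If only Cohort A contains patients who started on 3.5 mg/m2, the all-patient A-minus-B difference mixes two things: the difference between the cohorts at a common dose, and the effect of the second regimen on the Cohort A side. Because dose follows protocol version, that second part also carries any change over time in patients, sites or care.

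The one device that could separate them, adjustment for initial dose, depends on p-values. A covariate can distort the cohort contrast without reaching 0.10 alone or 0.05 in the model, especially at these sample sizes. Cohort faces the same selection rule.

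At stake is the reading of the BRCA objective. There is a second use too: Protocol 8.3.1 and SAP 8.9 allow cohorts to be pooled when their differences are judged not relevant, so a difference masked by dose could feed that decision.

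**Working it through.** **1. What the plan powers.** Protocol 8.2 gives two single-arm rules. Exact binomial checks:
- Cohort A, at least 17 of 53, 20% vs 40%: power 0.908.
- Cohort B, at least 12 of 64, 10% vs 25%: power 0.907.

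The stated power above 90% reproduces. Neither rule uses the A-versus-B difference, and no power is given for that difference.

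**2. Is Cohort B at 7 mg FD only?** The evidence is indirect.
- Both group lists omit Cohort B at 3.5 mg/m2. They were added when the SAP was updated for the amendments (SAP 14.1).
- The cohort minimums sum to 53 + 20 + 64 = 137, but Protocol 8.2 expects about 110. If A and A1 reach their minimums, 110 - 53 - 20 = 37 remain for B, which fits Cohort B stopping short.
- Against this, Protocol 5.2.1 does not exempt Cohort B from the version 3.0 dose, and the target of at least 64 still stands.

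The inference is reasonable but not established.

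**3. Do the regimens differ?** Starting dose = 3.5 x min(BSA, 2.0). At BSA 1.5, 1.7, 1.8 and 2.0 m2 this gives 5.25, 5.95, 6.3 and 7.0 mg. Below 2.0 m2 the milligram dose is under 7 mg. This does not convert into response points.

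**4. Shift in the A-minus-B difference.** Let s be the share of Cohort A starting on 3.5 mg/m2 and d the ORR on 3.5 mg/m2 minus the ORR on 7 mg FD. Then shift = s x d. The documents give neither, so both are assumed:

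| s | d = 0 | d = ±5 points | d = ±10 points |
|---|---|---|---|
| 25% | 0 | ±1.25 | ±2.5 |
| 50% | 0 | ±2.5 | ±5.0 |
| 75% | 0 | ±3.75 | ±7.5 |

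**5. Effect on the Fisher test.** Assume 53 vs 37 patients, ORR 25% at 7 mg FD in both cohorts (no BRCA effect), and d = +10 points. The chance of a significant result favouring A (two-sided 0.05) is 2.0% when s = 0, and 3.6%, 6.2% and 9.9% when s = 25%, 50% and 75%. With d negative, the shift hides a true difference instead.

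**6. Can selection drop dose while it matters?** Take Cohort A as 27 patients at 7 mg FD (ORR 40%) and 26 at 3.5 mg/m2 (30%), and Cohort B as 37 at 7 mg FD (25%). All values are assumed.
- All 7 mg FD patients: (10.8 + 9.25)/64 = 31.3%, against 30% at 3.5 mg/m2.
- Standard error: sqrt(0.313 x 0.687/64 + 0.30 x 0.70/26) = 0.107, so the expected z is 0.013/0.107 = 0.12. About 1.645 is needed for p < 0.10.
- All of Cohort A: (10.8 + 7.8)/53 = 35.1%, so A minus B is 10.1 points, against 15 at the same dose.

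The univariate screen is itself confounded by cohort, so here dose would very probably be excluded although it moves the difference by about 5 points.

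**7. What a same-dose contrast can deliver.** Assume 40% vs 25% and B = 37. Half-width of the 95% CI = 1.96 x sqrt(0.24/nA + 0.1875/37).

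| Cohort A patients | Fisher power | CI half-width (points) |
|---|---|---|
| 13 (25% at 7 mg FD) | 15% | 30 |
| 26 (50%) | 19% | 23 |
| 40 (75%) | 23% | 21 |
| 53 (all, both doses) | 29% | 19 |

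**The case against.** The best reply is that the SAP already deals with dose. The starting-dose subgroup tables for Cohort A cover response, ORR with an exact 95% CI, DR, PFS and OS. Cohort A at 7 mg FD will therefore be reported and can be set beside Cohort B. This stands, and it reduces the gap. What is missing is the difference itself with an interval, and an adjusted estimate that does not depend on screening.

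The comparison is also labelled exploratory, and the cohorts are not randomised. Cohort B includes patients of unknown BRCA status, and its responders found to carry a mutation are analysed with Cohort A (Protocol 7.1, SAP 2). Matching on dose cures none of this. That stands too, and limits what the change can achieve.

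It can also be said that restriction and adjustment overlap. If Cohort B has one dose, a logistic model with only cohort and dose has three parameters for three cells, so its cohort odds ratio equals the same-dose one. True; the restricted difference then mainly adds an absolute scale.

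Three stronger readings may tempt a reader, and the documents support none of them:
- *Cohort B certainly received only 7 mg FD.* This is inferred from safety-table groupings.
- *An A-versus-B difference can never be interpreted with respect to dose.* Both cohorts are listed at 7 mg FD, so confounding by dose is partial and a common-dose contrast exists.
- *The shift should be judged against a designed 15-point gap.* The 40% and 25% are the alternatives of two separate single-arm tests; no gap between cohorts was designed.

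**Conclusion.** The point holds in limited form. If the group lists describe the cohorts correctly, the exploratory A-versus-B comparison is partly confounded with starting dose and enrolment period, and the plan as written guarantees neither a same-dose difference nor a dose-adjusted one.

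The documents do not allow the bias to be sized or signed. The 0 to 7.5 points either way rests wholly on an assumed 25-75% share of Cohort A on 3.5 mg/m2 and an assumed 0 to 10 point ORR difference between regimens; it is zero if the regimens perform alike. The false-positive and power figures also assume 37 patients in Cohort B.

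This is a worthwhile, inexpensive improvement to a secondary, exploratory analysis. It does not touch the primary within-cohort ORR tests and implies no view on which dose is right.

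**What to change.** In SAP 6.2.2, for the A-versus-B comparison:

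1. Fit the logistic (ORR) and Cox (PFS, OS) models with Cohort and starting dose forced in, exempt from the 0.10 screen and from stepwise selection.
2. Report the difference between Cohort A at 7 mg FD and Cohort B at 7 mg FD with its 95% CI, as an estimate, beside the all-patient comparison.
3. Tabulate the number of patients by cohort and starting dose. This also settles whether Cohort B had one regimen.

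The cost is SAP wording and one set of tables, with no change to conduct. The same-dose interval is wider (half-width about 21 to 30 points against 19 with all of Cohort A, under the assumptions above) and power is low, so the result should be labelled descriptive. The text should also say that dose remains tied to calendar period and that other differences between these non-randomised cohorts are not removed.
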